5.2. General Methods

In Part 1 DB, as all participants randomized to treatment groups of etrasimod 2 mg QD and placebo will switch to open-label treatment of etrasimod 2 mg QD at Week 16, the treatment labels used for reporting DB visits up to Week 16 will be "Etrasimod 2 mg QD" and "Placebo" respectively. At the end of Part 1 OLE, when reporting OLE visits from Week 20 through Week 68, the treatment labels used will be "Etrasimod 2 mg QD" and "Placebo → Etrasimod 2 mg QD" respectively to differentiate these two treatment groups.

For Part 1 DB analyses up to Week 16, the following treatment comparison will be made at each timepoint, where applicable:

• Etrasimod 2 mg QD vs. Placebo.

The primary efficacy comparison for the primary endpoint of IGA response at Week 16 will be between etrasimod 2 mg QD and placebo. For analyses after Week 16 from Week 20 through Week 68 (Part 1 OLE phase), the following treatment comparison will be made at each timepoint,

• Etrasimod 2 mg QD vs. Placebo \rightarrow Etrasimod 2 mg QD.

For Part 2 OL Safety phase, there will only be one treatment group of etrasimod 2 mg QD, the label will be "Etrasimod 2 mg QD". There is no treatment comparison in Part 2. There will be no pooling of efficacy and safety data of Part 1 and Part 2 in this study.

Descriptive Summaries

In general, the data for all continuous endpoints will be summarized by treatment group and by timepoint in tables containing descriptive statistics (N as the number of participants evaluable for the endpoint at the timepoint, mean, standard deviation, standard error of the mean, minimum, 1^{st} , 2^{nd} (ie, median) and 3^{rd} quartiles and maximum) for actual and change from baseline (or percent change from baseline) values for those endpoints measured at baseline. In case when N=1 (ie, only one participant is available/evaluable for summary), standard deviation and standard error will be reported as "NA" (not applicable) while the remaining statistical parameters will have the same value as the mean. The data for all response-type binary endpoints will be summarized by treatment group and by timepoint in tables showing descriptive statistics: N, n (ie, number of responders), response rate, standard error (SE) of the response rate, and 95% confidence interval (CI) based on normal approximation, all expressed in %. If \hat{p} is the estimated response rate, then the 95% CI is calculated as:

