6.5.3. Vital Signs

Absolute values and changes from baseline in systolic and diastolic BP and pulse rate will be summarized by treatment group and time post-dose in accordance with the CaPS. The number and percent of participants with clinically significant change from baseline will be tabulated by treatment group.

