6.5.4. Electrocardiograms

Changes from baseline for the ECG parameters QT interval, heart rate, QTc interval, PR interval, and QRS complex will be summarized by treatment and time.

Changes from baseline for the ECG parameters HR, QTcF, PR interval, and QRS complex will be summarized by treatment and time. The frequency of uncorrected QT values above 500 ms will be tabulated.

The number (%) of participants with maximum post-dose QTcF values and maximum increases from baseline in the following categories will be tabulated by treatment.

 Table 6.
 Safety QTcF Assessment

Degree of Prolongation	Mild (ms)	Moderate (ms)	Severe (ms)
Absolute value	>450 – 480	>480 - 500	>500
Increase from baseline		30-60	>60

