Appendix 2. Data Derivation Details

Appendix 2.1. Definition and Use of Analysis Visit Windows in Reporting

There are two sets of analysis visit windows, one set for Part 1 (both DB and OLE phases) and another set for Part 2 (OL). For reporting purposes, the analysis visit windows will be used for efficacy and safety display that show by scheduled visits. Observations from all visits including scheduled, unscheduled and early termination visits will all be eligible for allocation to an analysis visit. If two or more observations fall into the same visit window, the observation closest to the target day will be used in the analysis. If there is a tie, the later observation will be used. However, for a participant who discontinues from the study early prior to Week 68 visit window in Part 1 (similarly to Week 52 visit window in Part 2), if two or more observations fall in the same visit window prior to Week 68 in Part 1 (similarly to Week 52 in Part 2), then the latest observation (rather than the observation closest to the target day) within this visit window will be used in the analysis for that visit window.

The analysis visit windowing will be applied after intercurrent events (initation of prohibited medications or discontinuation of study treatment, whichever is earlier) have been accounted for, that is, to the pre-intercurrent-event data and to all data separately (Appendix 3).

Table 8. Analysis Visit Windows for Part 1

Visit Label	Target Day ^a	Window Definition
Baseline	Day 1	Last non-missing assessment on or before Day 1 and prior to first dose of investigational product (ie, etrasimod or placebo)
Week 4	Day 29	Day 2 to Day 42
Week 8	Day 57	Day 43 to Day 70
Week 12	Day 85	Day 71 to Day 98
Week 16 ^b	Day 113	Day 99 to [Treatment Switch Day ^c or Day 126, whichever is smaller]
Week 20	Day 141	[Treatment Switch Day ^c +1 or Day 127, whichever is smaller] to Day 154
Week 24	Day 169	Day 155 to Day 196
Week 32	Day 225	Day 197 to Day 252
Week 40	Day 281	Day 253 to Day 322
Week 52	Day 365	Day 323 to Day 420
Week 68	Day 477	≥ Day 421

a. Target day is equal to the target week \times 7 days + 1 day.

b. All data collected on Week 16 visit, first open-label dose day (treatment switch day), will be included in ≤ Week 16 except for AE data, which will be included in ≥ Week 20. Any new treatment-emergent AE occurred on the day of first open-label dose (treatment switch day) will be included in ≥ Week 20.

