c. Day of first open-label dose at Week 16 = Treatment switch day (ie, treatment switch day = treatment switch date – date of the first dose +1), where treatment switch date is taken from the Treatment Dosing CRF, as the start date in the first entry of the Treatment Dosing log for the period of Week 16 to Week 20.

Note that the upper limit of the Week 16 visit window and the lower limit of the Week 20 visit window are defined uniquely for each of the participants in the study regardless of which treatment group the participants are randomized to.

If treatment switch day (ie, day of first open-label etrasimod dose) falls between Day 99 and Day 126, then the upper limit of the Week 16 visit window is the smaller of treatment switch day or Day 126, and the lower limit of the Week 20 visit window is the smaller of treatment switch day+1 or Day 127.

In the unlikely case if treatment switch day < Day 99, > Day126, or missing (eg, discontinuation of study treatment or study prior to Week 16), then the upper limit of the Week 16 visit window will be set to Day 126 and the lower limit of the Week 20 visit window will be set to Day 127.

Table 9. Analysis Visit Windows for Part 2

Visit Label	Target Day ^a	Window Definition
Baseline	Day 1	Last non-missing assessment on or before Day 1 and prior to first dose of etrasimod
Week 4	Day 29	Day 2 to Day 42
Week 8	Day 57	Day 43 to Day 84
Week 16	Day 113	Day 85 to Day 140
Week 24	Day 169	Day 141 to Day 210
Week 36	Day 253	Day 211 to Day 280
Week 44	Day 309	Day 281 to Day 336
Week 52	Day 365	≥ Day 337

a. Target day is equal to the target week \times 7 days + 1 day.

For safety data collected for participants who complete the 2-week and 4-week follow-up visits (Weeks 70 and 72 in Part 1 OLE, Weeks 54 and 56 in Part 2 OL Safety phase), available safety data will be summarized for these nominal visits.

For 12-Lead ECG collected on Day 1 during first-dose cardiac monitoring, the labels for timepoints can be "Day 1 Predose", "Day 1 1HR Postdose" to "Day 1 4HR Postdose".

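### SAP Table 8 counts vital signs and ECGs taken after a placebo participant's first open-label etrasimod dose as double-blind Placebo data

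*SAP*

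**What the plan says.** - SAP Appendix 2.1, Table 8, footnote b: "All data collected on Week 16 visit, first open-label dose day (treatment switch day), will be included in ≤ Week 16". AE data are the one exception; AEs that start on the switch day go to Week 20 or later.
- The Week 16 window in Table 8 is defined in whole days and closes on the switch day (at most Day 126). It has no cut at the time of dosing. The appendix states that these windows serve safety as well as efficacy displays by scheduled visit.
- SAP 5.2 introduces the two double-blind labels, Etrasimod 2 mg QD and Placebo, with the words "the treatment labels used for reporting DB visits up to Week 16 will be". The label Placebo → Etrasimod 2 mg QD applies from Week 20.
- Selection within a window (Appendix 2.1) takes the observation nearest the target day, and "If there is a tie, the later observation will be used". For a participant who leaves the study before the Week 68 window, "then the latest observation (rather than the observation closest to the target day) within this visit window will be used".
- The baseline row of Table 8 does split at the dose: "Last non-missing assessment on or before Day 1 and prior to first dose of investigational product".
- The Part 1 schedule of activities (Protocol 1.3.1) places the first open-label dose on site at Week 16. Vital signs are scheduled pre-dose and at 1, 2, 3 and 4 hours, and ECGs pre-dose and at 4 hours.
- SAP 6.5.3 gives the rule for blood pressure and pulse displays: "Absolute values and changes from baseline in systolic and diastolic BP and pulse rate will be summarized by treatment group and time post-dose". SAP 6.5.4 gives the rule for the QTcF table: "The number (%) of participants with maximum post-dose QTcF values and maximum increases from baseline in the following categories will be tabulated by treatment".

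**The concern.** The Week 16 visit ends the double-blind period and also starts etrasimod for the placebo arm. A window defined in whole days cannot separate the two. Readings taken up to four hours after a placebo participant's first etrasimod dose therefore sit in the double-blind Placebo column.

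The SAP is also inconsistent with itself. A bradycardia AE on the switch day is reported in the extension, while the heart rate behind it is reported as double-blind placebo data. Day 1 is split at the dose; Week 16 is not, although Protocol 10.10.3 applies the same first-dose monitoring at both visits.

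Protocol 2.3.1 describes the heart-rate reduction as largest on the first dosing day, so the misplaced readings are those where an effect is most expected. The Part 1 schedule has no other double-blind ECG visit after Day 1. The interim data cut (SAP 7) takes safety data through the Week 16 visit, and Protocol 4.1 names ECG and vital-sign changes among the inputs to the Part 2 decision. Placing first-dose readings in the placebo column would tend to narrow any apparent difference between the arms.

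**Working it through.** The documents give no figure for this point, so there is none to reproduce. The check applies the Table 8 rules to the scheduled Week 16 readings.

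**1. Switch-day readings per placebo participant entering the extension** (Protocol 1.3.1)
- Vital signs: pre-dose + 1, 2, 3, 4 h = 5 sets, of which 4 are post-dose.
- ECG: pre-dose + 4 h = 2, of which 1 is post-dose.
- All fall in the Week 16 window for any switch day from Day 99 to Day 126.
- Upper bound, if all 30 planned placebo participants continue: 30 × 4 = 120 vital-sign sets and 30 × 1 = 30 ECGs carry the wrong label.

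**2. Share of scheduled double-blind readings after the first study dose**
- Vital signs: Day 1 at 1–4 h (4) + Weeks 4, 8, 12 (3) + Week 16 pre-dose (1) + Week 16 at 1–4 h (4) = 12. Share: 4/12 = 33%.
- ECG: Day 1 at 4 h (1) + Week 16 pre-dose (1) + Week 16 at 4 h (1) = 3. Share: 1/3 = 33%.

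These are the readings that can feed a double-blind maximum or categorical table.

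**3. Which ECG becomes the Week 16 value in a by-visit display**
- Target is 16 × 7 + 1 = Day 113. The visit window of ±5 days gives Days 108–118, 11 possible days.
- At a regular visit both ECGs share one study day, so their distances from Day 113 are equal. The tie rule takes the later one, at 4 h post-dose, on all 11 days.
- The latest-observation rule for early study leavers gives the same choice.

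**4. Participant who dosed at home and returns within 3 days** (Protocol 6.5)

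Assume the same assessment was also taken at the first visit on day d, with the first open-label dose on day d + k, k = 1, 2, 3. Under the nearest-day rule a post-dose reading is selected when |d + k − 113| ≤ |d − 113|.

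| d | distance on d | distances for k = 1, 2, 3 | post-dose selected |
|---|---|---|---|
| 108 | 5 | 4, 3, 2 | 3 |
| 109 | 4 | 3, 2, 1 | 3 |
| 110 | 3 | 2, 1, 0 | 3 |
| 111 | 2 | 1, 0, 1 | 3 |
| 112 | 1 | 0, 1, 2 | 2 |
| 113–118 | 0 to 5 | always larger | 0 |

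Total: 14 of 11 × 3 = 33 combinations.

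**5. Effect on a by-visit mean**

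If a fraction f of the placebo arm enters the extension and the mean first-dose effect at 4 h is δ, the Week 16 placebo mean moves by f × δ. Neither value is in the documents. For illustration only, an assumed heart-rate effect of −5 to −10 bpm with f = 1 moves the mean by the full −5 to −10 bpm.

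**The case against.** The strongest reply is that the readings may never be collapsed to one per visit. SAP 6.5.3 summarizes vital signs by time post-dose and 6.5.4 summarizes ECGs by time, both under sponsor display standards that are not in these documents. Day 1 post-dose readings fall in no Table 8 window (Week 4 opens on Day 2), so they can only be shown by nominal time, and the same may be intended for Week 16. This has force for vital signs, where a clean pre-dose row may survive. It does not move the 1–4 hour rows out of the Placebo column. For ECGs the only timepoint labels offered concern Day 1: "For 12-Lead ECG collected on Day 1 during first-dose cardiac monitoring, the labels for timepoints can be" followed by Day 1 pre-dose and post-dose names.

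Second, SAP 6.5.3 and 6.5.4 do not tie the categorical tables to a phase, and the documents describe heart-rate and AV-conduction effects, not QTcF prolongation. Entry into the maximum-QTcF table is therefore possible, not certain, and harm there is not shown. SAP 7 does say that safety is summarized to the end of the double-blind phase for the interim analysis, so the route exists.

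Third, 4 of 12 and 1 of 3 count readings and do not measure bias. The 14 of 33 weights all day and lag pairs equally and needs the assessment to have been taken at the first visit. If the pre-dose readings are deferred to the return visit with the other cardiac monitoring, the same-day tie rule applies instead. Both limits stand.

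Fourth, safety analyses are descriptive, the reviewing team is unblinded, an external committee monitors safety, and the randomized Day 1 first-dose comparison is intact. That limits the damage but does not correct the label.

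**Conclusion.** The point holds. Nothing in either document overrides footnote b, so readings that follow a first etrasimod dose are assigned to double-blind Placebo. It affects up to 30 placebo participants: 4 of 5 vital-sign sets and 1 of 2 ECGs on the switch day. In any by-visit ECG display at a regular Week 16 visit, the placebo arm is represented by its 4-hour reading after a first etrasimod dose, set against continued etrasimod in the other arm. That row is then not a placebo comparison.

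The ECG-row conclusion assumes one value per visit. Entry into the maximum and clinically-significant-change tables is possible under the text but not established. The shift in heart rate, PR or QTcF cannot be sized from the documents. Efficacy (assessed before dosing), switch-day AEs, the Day 1 contrast and Weeks 4–12 vital signs are unaffected. This should be fixed, but it does not threaten the primary analysis.

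**What to change.** Amend footnote b so that, on the treatment switch day, only pre-dose assessments count as Week 16 or earlier. Then:

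- Assign that day's post-dose vital signs and ECGs to the extension under Placebo → Etrasimod 2 mg QD (and the matching label for the etrasimod arm), with Week 16 pre-dose and hourly post-dose timepoint labels parallel to those for Day 1.
- Exclude them from by-visit Week 16 selection, including the tie and latest-observation rules, and from the double-blind maximum-QTcF and clinically-significant-change tables.
- In the same edit, reconcile footnote b with the note that caps the Week 16 window at Day 126 when the switch comes later, since the two now place those data differently.

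The cost is a sentence in the footnote, a set of labels and the matching programming specifications, all before the interim data cut. No new data are needed: pre-dose and hourly readings are already scheduled as separate timepoints, and no visit or clinical procedure changes. A safety display starting at each participant's first etrasimod dose would be a useful addition but is not needed to correct this error.

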5.3. Methods to Manage Missing Data

In Part 1 DB phase, after accounting for relevant intercurrent events in the data sets (Section 2.2, Appendix 3) and visit windowing (Appendix 2.1) in the data, if a binary efficacy endpoint at a visit has missing value, it will be handled by setting the missing binary efficacy DMB02-GSOP-RF02 7.0 Statistical Analysis Plan Template 31-Jan-2022

endpoint to non-response. This method of handling missing binary efficacy endpoint is known as missing response as non-response (MR=NR). In general, if a continuous efficacy endpoint at a visit has missing value, it will remain missing and no imputation of this missing value will be performed in the datasets.

Under Estimand E1 (eg, IGA response at Week 16), after accounting for the occurrence of relevant intercurrent events in the dataset and in the FAS, missing binary efficacy endpoint at a visit will be set to non-response (ie, treatment failure). If intercurrent events have not occurred before a visit, and the binary efficacy endpoint at this visit has missing value, it will be set to non-response due to MR=NR. Under the Estimand E1a, since intercurrent events are not considered, if the binary efficacy endpoint at a visit has missing value, it will be set to non-response due to MR=NR.

For continuous efficacy endpoint analyzed under Estimand E2 (eg, percent change from baseline in EASI score at a visit), after accounting for the occurrence of relevant intercurrent events, the post-intercurrent-event data will be treated as missing, only pre-intercurrent event data will be included in the JTC method via multiple imputations (Section 5.2.2.1).

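### SAP visit windows mishandle a first open-label dose after Day 126 or before Day 99: a blinded Week 16 value can go to Week 20, or an open-label value can count as Week 16

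*SAP*

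**What the plan says.** Three statements in SAP Appendix 2.1 govern where the end-of-double-blind assessment is placed.

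- **Table 8** defines Week 16 as "Day 99 to [Treatment Switch Day ^c or Day 126, whichever is smaller". Week 20 starts on the day after the switch or on Day 127, whichever comes first.
- **The text below the table** covers the exceptions: "In the unlikely case if treatment switch day < Day 99, > Day126, or missing", "then the upper limit of the Week 16 visit window will be set to Day 126". The Week 20 window then starts on Day 127.
- **Footnote b** states: "All data collected on Week 16 visit, first open-label dose day (treatment switch day), will be included in ≤ Week 16". Only AE data are excepted; early and late switches are not.

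Three further rules decide what follows. The Week 12 window is "Day 71 to Day 98". On eligibility, "Observations from all visits including scheduled, unscheduled and early termination visits will all be eligible for allocation to an analysis visit". On selection, "If two or more observations fall into the same visit window, the observation closest to the target day will be used in the analysis"; for participants who leave the study early, the latest observation in the window is used instead.

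Under SAP Section 5.3, a "missing binary efficacy endpoint at a visit will be set to non-response (ie, treatment failure"). EASI percent change under Estimand E2 is multiply imputed instead (SAP Section 5.2.2.1).

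The protocol's Schedule of Activities puts Week 16 at Day 113 ± 5 and has the IGA and EASI done before dosing.

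**The concern.** The IGA and EASI precede the dose, so a value taken on the switch day is a double-blind outcome whatever the calendar day. An efficacy value from any later day is an open-label outcome. A windowing rule should keep that boundary, and the exception text does not.

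**Late switch (after Day 126).** The cap and the exception text put the pre-dose switch-day value in a window reported under the OLE treatment labels. Footnote b puts the same value in Week 16 or earlier. Two programmers could each follow the SAP and derive different primary-endpoint values.

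**Early switch (before Day 99).** The Week 16 window stays open for four weeks in which the participant is already on open-label etrasimod. For someone randomised to placebo, an etrasimod result could be analysed as the placebo outcome. No other rule removes it: the only intercurrent events are prohibited medication and discontinuation of study treatment (SAP Section 2.2.1 and Appendix 3), and starting open-label drug is neither.

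What is at stake is the Week 16 IGA response and EASI-75. Windowing is applied separately to the pre-intercurrent-event data and to all data, so the supportive Estimand E1a inherits the same allocation.

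**Working it through.** **1. The plan's own precision figures** (Protocol Section 9.5: 30 per arm, 39% and 9%). Half-width = 1.96 × √[p(1−p)/n].

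- Etrasimod: 1.96 × √(0.39 × 0.61/30) = 17.45%.
- Placebo: 1.96 × √(0.09 × 0.91/30) = 10.24%.
- Difference: 1.96 × √(0.39 × 0.61/30 + 0.09 × 0.91/30) = 20.24%.

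These reproduce the stated limit of 17.5% and the stated 20.2%.

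**2. How far outside the schedule a case must be.** The Week 16 visit runs from Day 108 to Day 118 (113 ± 5). Protocol Section 6.5 allows up to 3 more days when the participant has already dosed that day: 118 + 3 = Day 121. A Day 127 switch is therefore 9 days past the visit window. A Day 98 switch is 10 days before it opens.

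**3. The allocation rule applied literally to test schedules** (earlier visits on Days 29, 57 and 85).

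| Switch day | IGA/EASI days after Day 85 | Week 16 value | Where the switch-day value goes |
|---|---|---|---|
| 113, 118 or 126 | switch day, 141 | switch day | Week 16, correct |
| 121 | 118, 141 | Day 118 | no assessment on Day 121 |
| 127 | 127, 141 | none | Week 20; loses to Day 141 |
| 130 | 130, 141 | none | Week 20; loses to Day 141 |
| 130 | 130 only | none | reported as Week 20 |
| 130 | 113, 130, 141 | Day 113 | Week 20; loses to Day 141 |
| 95 | 95, 141 | none | Week 12; loses to Day 85 |
| 95 | 95, 120, 141 | Day 120 (open-label) | Week 12; loses to Day 85 |

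For the Day 127 switch, the distance to the Week 20 target is |127 − 141| = 14 days, against at most 5 for an on-schedule Week 20 visit. Where the Week 16 value is none, IGA response and EASI-75 are set to non-response.

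**4. Which statements conflict.** For a late switch, the Table 8 cap and the exception text agree with each other and disagree with footnote b. For an early switch, the value falls in Week 12, which is at or before Week 16, so footnote b is satisfied. The exception text does serve a purpose here: for a Day 95 switch, Table 8 alone would give a Week 16 window from Day 99 to Day 95. It cures that inversion by opening Week 16 to post-switch data.

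**5. Size.** One participant changes an arm's rate by 1/30 = 3.3 points. As an illustration with assumed counts near the design rates (unstratified normal approximation):

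- 12/30 vs 3/30: difference 30.0 points (95% CI 9.4 to 50.6).
- One etrasimod responder lost, 11/30 vs 3/30: 26.7 (6.4 to 47.0).
- One placebo responder lost, 12/30 vs 2/30: 33.3 (13.7 to 53.0).

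**The case against.** The window of Days 99–126 is roughly two weeks either side of Day 113, is pre-specified, and applies to both arms alike. Declining to call a Day 127 assessment Week 16 is a defensible choice, and two explicit statements support it against one general footnote. The protocol's own route to a delayed first open-label dose does no harm: all other Week 16 procedures are done at the original visit, so the value stays in Week 16. The early-switch error needs an unscheduled or early-termination assessment, because the next scheduled visit is Day 141 ± 5, beyond Day 126. In the late case only responders are affected. At the design rates the expected shift per affected participant is 0.39 × 3.3 = 1.3 points (etrasimod) or 0.09 × 3.3 = 0.3 points (placebo), against a 20.2-point half-width in a study with no hypothesis test.

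Most of this stands and limits the point to rare cases. It does not remove the point. A deliberate cap would need an exception in footnote b, and there is none. A cap also cannot justify placing a blinded value in an OLE window or an open-label value in a double-blind one.

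A reader might infer more than the documents support:

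- **That both cases contradict footnote b.** Only the late switch does.
- **That every late switch produces a non-responder.** It does so only when no other value lies in Days 99–126, and only for the binary endpoints; EASI percent change is imputed.
- **That the measured value is always discarded.** It is re-labelled to Week 20 or Week 12, and drops out only if the selection rule there prefers another observation.

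**Conclusion.** The point holds for two narrow cases. After a switch later than Day 126, the SAP gives conflicting instructions for a measured, on-blinded-treatment value. Following the cap scores the participant as a Week 16 failure on IGA response and EASI-75 if Days 99–126 hold nothing else. After a switch earlier than Day 99, the SAP is internally consistent, but it lets an open-label assessment stand as the randomised Week 16 result.

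The size is up to 3.3 points in one arm per misclassified participant, assuming 30 analysed per arm. The direction depends on the arm and the response. The documents give no frequency, the SAP expects such cases to be unlikely, and both require a visit well outside the protocol window. Nothing here shows that the primary estimate will be biased in practice. The reason to act is that this rule derives the primary endpoint, and choosing between conflicting statements after treatment codes are released would be a post hoc decision.

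**What to change.** Before unblinding for the interim analysis, reconcile Table 8, the exception text and footnote b in SAP Appendix 2.1 by stating:

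1. No efficacy observation after the treatment switch day may enter a double-blind window (Week 16 or earlier). No pre-dose observation on or before the switch day may enter an OLE window (Week 20 or later).
2. For a switch after Day 126 with no other value in Days 99–126, the pre-dose switch-day value is the Week 16 value, as footnote b implies. This applies up to a pre-specified outer day before the Week 20 target (Day 141), and such values are flagged in a listing.
3. The Day 126/127 limits alone apply when the switch day is missing.

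The outer day is needed. If Week 16 simply ran to the switch day without limit, a switch on Day 154 would start Week 20 on Day 155, after that window's own end on Day 154.

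Whether a value from before Day 99 may serve as Week 16 is the sponsor's choice and is not part of this change.

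The cost is a few sentences of SAP text, a small change to the windowing code and one listing. The downside is that a few Week 16 values will come from off-target days.
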